#### **4.4.1 Data and Safety Monitoring**

This is a JHU-investigator-sponsored IND trial. Data and safety monitoring will follow DSMP Level 2 per the SKCCC Data Safety Monitoring Plan. The PI shall internally monitor the progress of the trial, including review and confirmation of all safety/treatment-related outcomes, response assessments, safety reports and/or any related source documentation. PI shall also establish additional external data/safety monitoring oversight (DSMB, etc), if required by IND-sponsor and detailed within protocol. IND-sponsor is ultimately responsible for external monitoring of JHU site, and also all subsites if JHU is coordinating center. Authorized representatives of the Coordinating Center may visit the satellite sites to perform audits or inspections, including source data verification. The purpose of these audits or inspections is to systematically and independently examine all trial-related activities and documents to determine whether these activities were conducted and data were recorded, analyzed, and accurately reported according to the protocol, Good Clinical Practice (GCP), and any applicable regulatory requirements.

The Data Safety Monitoring Board (DSMB) for this clinical study will contain a minimum of five members, including at least one oncologist, a statistician, and a lay representative. Members may not have a conflict of interest with any aspect of the clinical trial. The DSMB will provide a written recommendation to the IND Sponsor and Protocol Chair after each meeting. In turn, the study team will forward these summaries to the JHU IRB, and JHU SKCCC SMC. The operating plan of the DSMB will be as follows:

- Meetings will be held at least semi-annually, and potentially more frequently if needed.
- Meetings will be conducted in-person or via video/teleconference, with a participant sign-in sheet collected at each meeting. The Protocol Chair and study staff may attend the open portion of this meeting to review data and answer any question the DSMB might have).
- Approximately one week prior to each DSMB meeting, the study team will submit the following items to DSMB members for review and discussion at the meeting:
  - A summary of the clinical trial's progress to date;
  - The latest IRB-approved protocol and informed consent;
  - A summary of all adverse events, serious adverse events, deaths, and withdrawals to date;

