### **5.2 Blinding**

The double-blind portion of the study will end when every subject has either completed the study, been treated for 48 weeks, or discontinued the study. A subject is considered to have completed the study if he experiences PSA progression as defined in section 5.4. A subject will also be considered to have completed the study if they have not experienced PSA progression but remain on-study at the time the study ends at 48 weeks. Patients will not be informed if they are on the MPX or placebo arm. At protocol defined progression or completion of 48 weeks of treatment, patients will be offered an additional four 12-week cycles of MPX treatment, and will come for a visit every 12 weeks, without correlates but with PSA drawn every 12 weeks. Patients who come off study for any other reason will not be offered open label, extension MPX. Subjects will have an end of study visit and are required to have CT and bone scans prior to beginning the open label extension, and at discharge.

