### **7.3.2 All Adverse Events**

AEs will be defined with the NCI-CTCAE v5.0. All AEs, both related and unrelated, will be recorded on the appropriate study-specific CRFs, including the following information:

- Specific type of reaction in standard medical terminology
- Severity
- Relatedness
- Duration, including onset, of the event
- Description of treatment action or change in study drug administration or dose
- Resolution

Adverse events should be recorded from the start of treatment with MPX through one week following the last dose of study drug. Details of changes in AEs should be recorded even if they occur after the protocol prescribed follow-up. Investigators should follow-up subjects having serious or related AEs until the resolution of the event. Details of the resolution will be recorded in the CRF.

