 **Primary discontinuation reason and sampling:** If patient leaves the study for any reason prior to 24 weeks but > 12 weeks on trial, please record whether DC reason was patient meeting protocol defined progression (defined in Sec. 5.4 of this protocol) or DC reason was investigator judgement. If reason was protocol-defined progression, record whether there was pain, metastases on bone or CT scan and/or PSA progression. Also collect serum and urine for correlative studies, and perform CT and bone scans unless scans and patient samples have been collected in the past 8 weeks.

 **Pre-trial PSA's:** It is important to have 3 pre-trial PSA values (please refer to inclusion criteria #3 and #4) prior to day 0 and to collect a day 0 PSA value for on-study calculations.

 **Serum correlative samples:** One tube at original screening of 500 patients; three tubes at baseline, 12 weeks, 24 weeks, 36 weeks, 48 weeks and progression for patients on MAP trial.

 With **medical history** record prior prostatectomy, prior radiation (brachytherapy, SBRT, etc.) plus start and end dates of any prior hormonal therapy including name of drug. Please also state alcohol and smoking intake.

 **Open label extension:** For patients discharged prior to 48 weeks, open label MPX drug will be offered only to patients who meet protocol defined progression per Section 5.4, patients with radiographic progression (metastatic disease) are excluded.

 **MnSOD2 sample:** All 500 patients should get genotype (5ml blood).

 **Comprehensive metabolic panel** to include measurement of sodium, potassium, chloride, bicarbonate, BUN, creatinine, glucose, total bilirubin, calcium, total protein, albumin, AST, ALT, and alkaline phosphatase

 **Brief physical examination** includes cardiovascular, pulmonary, abdominal and Symptom-directed; includes investigating any new abnormalities and weight. Interval history includes any hospitalizations, illnesses, changes in medication

 **Eligibility:** All inclusion/exclusion criteria should be assessed at screening and confirmed prior to randomization

 **Drug compliance:** Compliance will be assessed by reviewing both returned # of pills and pill diary

 **Follow-up Visit:** The last visit will be 28 days (± 3 days) following last dose of study drug.

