We expect the average DTs of patients enrolling on this study to be in the range of 6 to 15 months, which correspond to average log slopes of 0.1155 ng/mL/month and 0.0462 ng/mL/month respectively. The historical post-treatment average slope estimates from the previous Hopkins trial were 0.033 ng/mL/month (average PSA-DT of 21 months) on the MPX arm and 0.083 ng/mL/month (average PSA-DT of 8.4 months) on the control arm. We have powered this study using the difference in these historical estimates as the clinically relevant post-treatment difference to be detected in this study: 0.05 ng/mL/month (or a PSA-DT difference of 12.6 months). It should be noted that for the same log slope difference between treatment arms, if the average post-treatment PSA rates of change are greater (steeper slopes), the detectable difference in DTs would be smaller and if the rates of change are less (slopes are less steep) the detectable DT difference will be larger.

**Randomization:** Stratified randomization will be performed to maintain balance between the arms as much as possible. Stratification will be by pretreatment PSADT ( $\leq 9$  or  $>9$  months) and Grade Groups (Grade Groups 1 and 2, equivalent to Gleason  $\leq 3 +4$ , and Grade Groups 3, 4 and 5, equivalent to Gleason  $\geq 4 +3$ ). Block randomization, with varying block sizes, will be used to ensure reasonable balance between the arms. Randomization assignments will be generated by the study statistician prior to initiation of the study using an R (version 3.4), and made available to the study team through the study electronic database.

**End of Study:** The date the study ends for the purpose of the final analysis is the date at which all randomized subjects have either completed the study or prematurely discontinued treatment and withdrew. This date will be designated as the primary analysis date for data cutoff and for all statistical analyses of efficacy and safety. Following the collection and adjudication of all data for all randomized subjects (follow-up up to and including the primary analysis date for data cutoff, the study blind will be broken (Section 5.2, Blinding).

**Primary Objective:** Determine if men who display the AA genotype of MnSOD and supplement their diet with MPX have greater changes in PSA slope following treatment compared to men that do not supplement with MPX.

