**Disease Progression (Metastatic disease):** The distribution of time to disease progression will be estimated using Kaplan-Meier method for the treatment groups combined and separately. The stratified logrank test will be used to test the hypothesis that the time to disease progression distributions for the 2 treatment groups are the same. The same stratification factors used for the randomization will be used to stratify the logrank test.

**Toxicity Assessments:** Safety analyses will be performed on all subjects that received at least one dose of MPX. The proportion of toxicities by type and grade according to the Common Terminology Criteria for Adverse Events (CTCAE) version 5.0 will be reported with exact binomial 95% confidence intervals for each arm of the study.

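### A single safety cut-off at the end of the blinded phase leaves the late open-label MPX exposure, and the last men's post-dose follow-up, out of every planned toxicity table

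*Combined protocol and SAP*

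**What the plan says.** The End of Study paragraph of section 11 sets the data cut-off at the point where every randomised man has either completed the study or stopped treatment early and withdrawn. It continues: "This date will be designated as the primary analysis date for data cutoff and for all statistical analyses of efficacy and safety".

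Section 5.2 says what completion means: "A subject is considered to have completed the study if he experiences PSA progression as defined in section 5.4". A man who reaches 48 weeks without progression has also completed. After either event, "patients will be offered an additional four 12-week cycles of MPX treatment, and will come for a visit every 12 weeks". Footnote 7 of the Study Calendar narrows this for men who leave before week 48: "open label MPX drug will be offered only to patients who meet protocol defined progression per Section 5.4", with radiographic progression excluded.

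Collection of adverse events (AEs) does not stop at the cut-off. Section 7.3.2 states: "Adverse events should be recorded from the start of treatment with MPX through one week following the last dose of study drug". The Study Calendar also schedules an AE assessment at the open-label visits and at the visit 28 days after the last dose. The DSMB receives "A summary of all adverse events, serious adverse events, deaths, and withdrawals to date".

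The planned toxicity analysis is in section 11.2: "Safety analyses will be performed on all subjects that received at least one dose of MPX", and the proportions by type and grade "will be reported with exact binomial 95% confidence intervals for each arm of the study". Section 11 does not mention the open-label extension.

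**The concern.** Taken together, these provisions put the only planned safety analysis up to 48 weeks before the last possible dose of MPX. The extension is the only MPX exposure for men randomised to placebo, and it holds all exposure beyond 48 weeks in this trial. Part of it is collected from men taking eight capsules a day and then tabulated nowhere.

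Two related gaps follow. The last men to finish blinded treatment have their one-week AE window and 28-day visit after the cut-off, so a little blinded-phase safety follow-up is also dropped. And section 11.2 does not say whether extension events that fall before the cut-off count, or under which arm. If they are counted by randomised arm, events that placebo men have while taking MPX go into the placebo column.

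**Working it through.** **Inputs.** 80 men randomised 1:1, with 48 weeks of blinded treatment (section 5); up to 48 weeks of extension (section 5.2); 4 years of accrual and another year of follow-up (section 11, Sample size and accrual). Accrual shape and extension uptake are not given, so they are assumed and varied.

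**The plan's own timeline.** 48 weeks = 11.04 months. Accrual plus blinded phase = 48 + 11.04 = 59.0 months, against the 60 stated, so the planned duration fits a cut-off at the end of the blinded phase. The last extension could end at 59.04 + 11.04 = 70.1 months, and its 28-day visit would fall at 71.0 months.

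**Base case: even accrual, full uptake, 48 blinded weeks for all.** A man entering at month e ends his extension at e + 22.08. Time lost after the cut-off is max(0, e − 36.96).
- Fraction of men cut: r = 11.04/48 = 0.230, and 80 × 0.230 = 18.4 men (about 9 of them ex-placebo: 40 × 0.230 = 9.2).
- Share of extension time cut: r/2 = 11.5%. In man-months, 80 × 11.04 = 883.1 in total, of which 101.5 are lost.

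**Other assumptions**

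| Assumption | Men cut | Share of extension time cut |
|---|---|---|
| Accrual falling linearly to zero over 48 months: r²; r²/3 | 4.2 | 1.8% |
| Accrual rising linearly from zero: 1 − (1 − r)²; r − r²/3 | 32.6 | 21.2% |
| Even over 24 months | 36.8 | 23.0% |
| Even over 36 months | 24.5 | 15.3% |
| Even over 72 months | 12.3 | 7.7% |
| Even over 48 months, half uptake | 9.2 | 11.5% |
| Even, 20% progress early and start the extension between weeks 14 and 48 (simulated) | 17.2 | 10.3% |
| Even, 40% progress early (simulated) | 15.9 | 9.0% |

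**Related AEs lost.** Section 2.2.6 reports 6 of 102 men on MPX with possibly related AEs in phase II (5.9%; exact 95% interval 2.2% to 12.4%). Section 2.2.3 gives 112 men randomised 1:2:2, which implies 112 × 4/5 = about 90 on MPX (6/90 = 6.7%). The documents do not reconcile the two. The rate pools both doses over an unstated duration; applying it per 48-week extension is an assumption.
- Full-extension equivalents lost in the base case: 80 × 0.115 = 9.2.
- Men with a related AE lost: 9.2 × 6/102 = 0.54 (0.20 to 1.14 over the exact interval), or 9.2 × 6/90 = 0.61.
- At the extremes of accrual shape: 80 × 0.018 × 6/102 = 0.08 and 80 × 0.212 × 6/102 = 1.0.

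**Placebo column.** If extension events before the cut-off are counted by randomised arm, ex-placebo men contribute 40 × (1 − 0.115) = 35.4 extension equivalents, or 35.4 × 6/102 = about 2 men with an MPX-related AE listed under placebo. The assumptions are the same.

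**The case against.** The strongest reply is that little depends on this. The trial has no safety objective. The related events in phase II were grade 1 or 2. Late extension events still reach the DSMB, the serious-event reports and the FDA. All of that stands, and it is why the point is minor. Those channels are oversight, however, and do not replace the toxicity table with exact intervals that section 11.2 plans.

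It could also be said that calling the date primary implies a later analysis. None is specified, and the sentence covers all statistical analyses and names safety. The safety stopping rule in section 11 is no substitute either: it works by arm, is tabulated to 39 patients, and does not say whether extension men are included.

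A reader might infer something stronger: that the toxicity table covers the blinded phase only, so that all 883 man-months of extension go untabulated. The documents do not support this. Section 11.2 sets no such limit, and its safety set, read literally, takes in placebo men once they start MPX. What the text does establish is the loss of the tail, plus silence on how the earlier extension events are assigned.

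**Conclusion.** The point holds as a minor one. A stated rule, not merely a missing detail, drops safety data that the trial collects. With even accrual over 48 months and full uptake, about 18 of 80 men lose part of their extension, or 11.5% of open-label exposure; across the assumed accrual shapes at that length the share runs from about 2% to 21%. The expected loss is about half a man with a related AE if the phase II rate carries over. Actual uptake will probably be lower, because men with radiographic progression and those who leave early for reasons other than progression are not offered open-label MPX. That lowers the number of men cut but not necessarily the share.

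The randomised efficacy comparison and its power are unaffected. Blinded-phase safety is touched only through the post-dose follow-up of the last men to finish. It would be wrong to conclude that late events escape safety oversight or that the trial's validity is threatened.

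**What to change.** Keep the section 11 date for efficacy. Then make two changes:

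1. State that the by-arm toxicity table in section 11.2 covers the blinded phase, including each man's one-week post-dose AE window and, for men who do not enter the extension, the 28-day visit. Ex-placebo men's events on MPX then stay out of the placebo column.
2. Add one descriptive open-label safety table, locked after the last man's 28-day visit. Report toxicities by type and grade with exact binomial 95% intervals, separately for ex-placebo men from their first MPX dose and for ex-MPX men beyond the blinded phase.

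The cost is a few sentences in section 11 and one later run of an existing table, about 52 weeks after the efficacy cut-off (48 + 4). No new visits or data are needed, the AE window does not change, and the efficacy report need not wait.

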**Sample size and accrual:** This two arm randomized study will determine if there are differences in the change in PSA slope (post supplementation minus pre supplementation) between patients supplementing with MPX (Arm A) and patients that are not (Arm B). The accrual rate for each site is expected to be 1 patient per month. With 16 to 17 sites, is expected that we could accrue 500 patients over 4 years, for which we will have baseline MnSOD genotype and baseline antioxidant status, of which approximately 80 would be of the required AA genotype and eligible for randomization to MPX or placebo. Overall the study would take 4 years of accrual and another year for follow-up. PSA slope will be defined by the linear regression line of the natural log of PSA (in ng/mL) against time (in months). The primary statistical analysis will be an analysis of covariance (ANCOVA) to compare the two arms at the final analysis, adjusting for baseline PSA slope. Implications of the sample size are given based on simulations which include a single interim analysis for futility midway through the trial. The predictive probability approach for the futility analysis is described in the interim analysis section below. Based on the previous study of MPX at Hopkins, we conservatively estimate that the difference in the post-treatment PSA slope (MPX minus placebo), adjusting for pre-treatment PSA, in this group of patients with the AA genotype will be -0.05 with the MPX arm having lower post-treatment slopes (MPX slope 0.033 ng/mL/month versus untreated 0.083 ng/mL/month). Patients with the AA genotype will be randomized to MPX (Arm A) and placebo (Arm B) in a 1:1 ratio. Using a two sided 5% type I error allowance, a sample size of 78 (39 per arm), and minimal correlation between the pre and post treatment PSA slopes, this study will have 83% power to detect a difference in post-study PSA slope of -0.05. Use of the ANCOVA design with covariate adjustment for pre-treatment PSA slope will tend to increase the power depending on the level of the correlation between paired PSA slope measurements (i.e., pre- and post-treatment). As an example, for a correlation ( $\rho$ ) of 0.30, the power would increase to 87%.

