**Interim analysis for primary objective:** We plan to monitor the primary efficacy objective for futility once, after treating half the planned number of patients (i.e., 39), using a predictive probability approach. The ANCOVA analysis for the primary objective is a linear regression using the post treatment PSA slope as the outcome and study arm and baseline PSA slope as covariates. The monitoring plan is based on calculations of the likelihood of a significant result if the trial were to continue to the end. At the time the trial is monitored, 100 simulations of the future results of the trial will be generated and analyzed. If the probability that the trial would end with a significant result falls below a cut off value, the study will be stopped for futility. In Bayesian linear regression, all the parameters are given a prior distribution. A common objective

prior for linear regression is the g-prior of Zellner. This prior uses the covariate information in the data to specify the prior variance for the regression coefficients. An inverse-gamma prior distribution is typically used for the residual variance,  $\sigma^2$ . We will use information obtained at the time of the interim analysis to describe the distributions of these parameters.

The interim analysis will occur after 50% of the patients ( $m=39$ ) have been treated and assessed for post-treatment PSA slope. At this time the ANCOVA model will be fit and the variance of the residuals,  $SSR_g$ , and the posterior distribution of the regression (ANCOVA) coefficients  $\beta$  will be calculated using the g prior with  $g = m$ . From this information, we predict the results of the trial by simulating the remaining future patients' data from the predictive distribution and performing an ANCOVA analysis on the combined interim data and simulated data. We will base the predicted probability of ultimately finding a significant difference on 100 simulations. The following steps will be used to generate the  $i^{th}$  simulated value.

1. Generate  $\sigma^{2(i)}$  from its inverse-gamma posterior.
2. Generate  $\beta^{(i)}$  from its (conditional) posterior distribution.
3. Generate  $\tilde{Y}_j, j=1, \dots, n-m$  from  $N(X_j \beta^{(i)}, \sigma^{2(i)})$
4. Perform the final ANCOVA analysis based on the interim data and the predicted data.
5. Repeat for the required number of simulations predicting the final outcome (100).

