6. Calculate the predicted probability of rejecting the null hypothesis at the end of the study.

If interim analysis simulations indicate that the probability of a successful trial would be less than 10%, we will consider stopping the trial for futility. The table below gives the operating characteristics of the monitoring plan based on 2000 simulations for different scenarios, each scenario corresponding to different treatment effects and different levels of correlation between the pre-treatment and post-treatment PSA slope. The seventh row shows results using the hypothesized treatment effect of a mean difference of -0.05 with a standard deviation of 0.075, and minimal correlation. We do expect some correlation between pre and post-treatment values, so power will tend to increase with increasing correlation. The significance level for the final analysis is 0.05. Scenarios 1-3 give operating characteristics under the null (no treatment effect).

**Table 1.** Operating characteristics of monitoring rule from 2000 simulated studies with one interim analysis based on 100 predicted study conclusions and final analysis based on an ANCOVA model. Simulations use a *g*-prior with  $g=39$  (i.e. the sample size at the time of the interim analysis). All simulations assume the standard deviation of post-treatment PSA slope is 0.075.

Scenario	Treatment Effect	Correlation (pre- and post-treatment measures)	Stop for Futility %	Would have stopped for Futility and would have Rejected %	Overall studies rejecting Ho %
1	0.0	0.1	34.0%	0.10%	4.3%
2	0.0	0.2	33.5%	0.35%	5.6%
3	0.0	0.3	34.5%	0.20%	4.4%
4	-0.025	0.1	21.9%	1.00%	31.8%
5	-0.025	0.2	20.4%	0.80%	30.6%
6	-0.025	0.3	17.5%	1.40%	35.0%
7	-0.050	0.1	4.5%	1.25%	82.7%
8	-0.050	0.2	4.4%	0.75%	81.9%

9	-0.050	0.3	3.0%	0.95%	87.3%
10	-0.075	0.1	0.4%	0.30%	98.8%
11	-0.075	0.2	0.4%	0.20%	99.1%
12	-0.075	0.3	0.2%	0.15%	99.7%

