### 11.1 Analysis Plans for Primary Objective

**PSA Slope:** Eligible patients must have a rising PSA with a minimum of 3 time points but up to 17 time points (2 rises at least 21 days apart) within the 12 months prior to study initiation (this could include the PSA measurement taken at the screening visit, but not at the baseline day 0 study visit). The pre-treatment slopes will be calculated based on these data prior to baseline (day 0). A minimum of three time points but up to five time points will be used for calculating on-study slopes: baseline, 12, 24, 36, and 48 week assessments. All data points will be used unless an assessment is unavailable, in which case the remaining time points will be used. There must be a minimum of three data points, and there will be no imputation of missing PSA values.

The primary objective will be based on the intent-to-treat (ITT) population and assessed with an ANCOVA model, with post-treatment PSA slope as the independent variable and study arm and baseline PSA slope as covariates. A two-sided t test at the 0.05 significance level will be used to determine if, adjusting for baseline, the post-treatment PSA slope has been reduced with MPX supplementation (Arm A). Scatterplots of post treatment PSA slope by baseline slope will be used to visualize the fitted ANCOVA model. Boxplots of the observed changes will also be used to visualize the results.

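### The futility rule counts a significant result in either direction as success, so it lets a trial continue when MPX looks worse and about halves the chance of stopping when there is no effect

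*Combined protocol and SAP*

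**What the plan says.** Section 11 (Interim analysis for primary objective) plans one futility look, after half of the patients have been treated and assessed for on-study slope. It uses Bayesian predictive probability with a g-prior. The decision sentence reads "If the probability that the trial would end with a significant result falls below a cut off value", after which the study stops. Step 6 of the algorithm defines the quantity: "Calculate the predicted probability of rejecting the null hypothesis at the end of the study". The number of draws is also fixed: "We will base the predicted probability of ultimately finding a significant difference on 100 simulations". No step refers to the sign of the treatment coefficient.

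The null hypothesis in question is the one tested at the end, and Section 11.1 states: "A two-sided t test at the 0.05 significance level will be used". The text above Table 1 sets the cut-off at 10% and applies it to the chance that the trial succeeds, without defining success.

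The aim is directional. Section 1.1 asks whether slope falls more on MPX, the sample size paragraph expects lower slopes on MPX, and Section 11.1 tests whether MPX has reduced the slope. The design case is a "mean difference of -0.05 with a standard deviation of 0.075".

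Table 1 reports futility stopping of 34.0%, 33.5% and 34.5% in the three no-effect scenarios. All other scenarios favour MPX. None has MPX worse than placebo.

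**The concern.** A futility look exists to end a trial that is unlikely to show benefit. If success means rejection in either direction, the predicted probability is lowest when the interim difference is near zero and rises again as placebo pulls ahead. The further MPX falls behind, the more firmly the rule says to continue.

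Two things are at stake. First, efficiency: with no effect, about two thirds of trials would run to the end, where a directional rule would let about one third do so. Accrual is planned over 4 years, with about 500 men genotyped to find 80. Second, the number handed to the decision-makers is misleading, because it can report a high chance of success when placebo is winning.

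No other written rule covers this. The toxicity rule in Section 11 counts toxicities. The DSMB package in Section 4.4.1 lists trial progress, protocol and consent, adverse events, deaths and withdrawals, and the stated ground for halting is safety. Section 7.1.1 excludes expected disease progression from adverse events.

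**Working it through.** **Inputs from Section 11 and Table 1.** Final n = 78 (39 per arm), interim m = 39, 1:1 allocation, two-sided alpha 0.05, SD of post-treatment slope 0.075, planned effect -0.05, pre/post correlation 0.1 to 0.3, g = 39, 100 draws, cut-off 10%.

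**Stated power.** A two-sample t test with 39 per arm, difference 0.05 and SD 0.075 has power 82.8% (noncentral t). The plan says "this study will have 83% power to detect a difference in post-study PSA slope of -0.05", so the inputs are understood correctly.

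**Closed-form check of the rule.** Let z be the interim statistic, positive when MPX is better. With a flat prior and half the information in hand, the final statistic given z is approximately N(√2·z, 1).

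- Either direction: PP = 1 - Φ(1.96 - √2·z) + Φ(-1.96 - √2·z). PP < 0.10 when |z| < 0.461. Under no effect, P(|Z| < 0.461) = 35.5%.
- MPX better only: PP = 1 - Φ(1.96 - √2·z). PP < 0.10 when z < 0.480. Under no effect, P(Z < 0.480) = 68.4%.

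The either-direction probability is symmetric: it is 29% at z = +1 and also at z = -1, but 5% at z = 0.

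For other effects at correlation 0.1, the residual SD is 0.075·√(1 - 0.1²) = 0.0746 and the interim standard error is 0.0746·√(4/39) = 0.0239. Effects of 0.025 and 0.05 are then 1.05 and 2.09 standard errors. Either-direction stopping is 21.3% at -0.025, 4.6% at -0.05 and 0.4% at -0.075. Table 1 gives 21.9%, 4.5% and 0.4%.

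**Simulation of steps 1 to 6.** ANCOVA on arm and baseline slope, g-prior with g = 39, 100 predictive completions, 15,000 trials per scenario. The documents do not give three of the settings, so these were assumed: an inverse-gamma prior with 1 degree of freedom centred on the interim residual variance, baseline slope SD 0.075, and control mean slope 0.083. The no-effect results barely moved when the prior weight or the means were changed (34.3-34.9% and 68.3-68.5%).

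| True effect (correlation) | Stop, Table 1 | Stop, either direction | Stop, MPX better only |
|---|---|---|---|
| 0 (0.1) | 34.0% | 34.7% | 68.5% |
| 0 (0.2) | 33.5% | 34.8% | 68.6% |
| 0 (0.3) | 34.5% | 33.8% | 68.0% |
| -0.025 (0.1) | 21.9% | 21.8% | 29.5% |
| -0.05 (0.1) | 4.5% | 5.0% | 5.9% |
| +0.025 (0.1) | not shown | 20.9% | 93.4% |
| +0.05 (0.1) | not shown | 4.8% | 99.3% |

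Table 1 rests on 2,000 runs, so 34% has a standard error of √(0.34·0.66/2000) = 1.1 points. A true rate of 68% cannot produce it.

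Two more no-effect columns agree. Stopped but would have rejected is 0.10-0.35% in Table 1; the closed-form model gives about 0.26% for either direction and 2.6% for MPX only. Overall rejection is 4.3-5.6% in Table 1; the same model gives about 4.8% and 2.4%.

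Power at -0.05 and correlation 0.1 is 81.0% under the either-direction rule and 80.8% under the directional one (Table 1: 82.7%). Some correlation-0.3 rows match less closely: at -0.025, stopping is 20.9% against 17.5% and rejection 31.5% against 35.0%; at -0.05, rejection is 84.5% against 87.3%. This does not affect the no-effect comparison.

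**Behaviour when MPX trails.** Under no effect, 66% of interim looks with an estimate unfavourable to MPX continue, and all of those at least 1 standard error in the wrong direction continue. With the directional rule none do.

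**Noise from 100 draws.** Near the cut-off the standard error is √(0.10·0.90/100) = 3 points. Stopping needs 9 or fewer successes in 100. If the true predictive probability is 12%, a run says stop 22.6% of the time; if it is 8%, a run says continue 27.8% of the time.

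**The case against.** The strongest reply is that nothing in the primary inference is damaged. Type I error stays near 5%, the final test and estimate are unchanged, and Table 1 openly shows 34% stopping under no effect. That is right. The defect lies in the futility look, not in the final analysis.

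The saving in patients is also smaller than a naive count suggests. If accrual stopped at 39, expected N under no effect would be 64.5 as written (39·0.347 + 78·0.653) and 51.3 with the directional rule, a gap of about 13. But slopes take up to 48 weeks. With even accrual of 78 to 80 men over 48 months (about 1.6 to 1.7 per month), patient 39 is fully assessed at about month 34 to 35, when about 57 are already randomized. Only 21 to 23 men then remain, and the gap falls to about 7 or 8. This stands, although a stop would also shorten treatment for men still on study.

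The documents are unclear on whether the rule binds: one sentence says the study is to stop, a later one that stopping will be considered. The sponsor might use discretion if MPX trailed badly. Discretion does not repair a success probability that rises as placebo wins.

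Two-sided success could be a deliberate choice, so that harm from a product already on sale can be shown. The plan states no such aim and calls the rule futility.

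Finally, Table 1 was itself generated with 100 draws, so its figures already include that noise. A single run differs from the exact rule in about 8.6% of no-effect trials and 1.4% at the planned effect. The draw count is a secondary point.

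**Conclusion.** The concern holds. As written and as simulated, the rule treats significance in either direction as success. Under no effect it stops about 34% of trials where a directional rule would stop about 68%. If MPX is worse by 0.025 or 0.05 it stops about 21% or 5%, against 93% or 99%. It does not continue every trial in which MPX trails: about a third of unfavourable looks under no effect still stop. Continuation becomes practically certain once the estimate is about 1 standard error or more in the wrong direction.

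The figures rest on SD 0.075, a look at exactly half the information, the 10% cut-off applied as a rule, and the prior settings stated above. The no-effect contrast does not depend on those settings in any material way. The rule should be corrected before the interim look, because it fails at the one task it is there to do.

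**What to change.** In steps 5 and 6, count a simulated trial as a success only if the final test is significant and the MPX coefficient is negative (lower slope on MPX). Use the same definition where the text above Table 1 speaks of the trial succeeding. State in one place whether the rule binds or is advisory.

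Re-run Table 1, restate the stopping and rejection columns, and add scenarios with MPX worse than placebo, for example +0.025 and +0.05.

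Raise the draws at the real interim from 100 to 10,000, which cuts the standard error near the cut-off from 3 points to 0.3. Even 1,000 draws would bring it to about 0.95 points.

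The cost is a short change of wording and a re-run of an existing simulation. At the planned effect, stopping rises by about 1 point (5.0% to 5.9%) and power falls by about 0.2 points (81.0% to 80.8%). The real trade-off is that a trial trending towards harm will rarely run long enough to prove harm. If the sponsor wants to keep that ability, the plan should say so and justify it.
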